2.4.5.1 Analysis of primary efficacy endpoint(s)

The RR will be summarized using descriptive statistics. A 90% 2-sided confidence interval will be computed using Clopper-Pearson method. BOR will be summarized descriptively. For mCRPC cohorts, PSA response will also be summarized using descriptive statistics.

2.4.5.2 Analyses of secondary efficacy endpoints

The secondary efficacy endpoints are:

- Tumor burden change: the best percent-change from baseline in tumor burden will be summarized and presented graphically for patients with measurable disease at baseline. In addition, a summary of the AUC and the time-adjusted AUC of percent-change from baseline in tumor burden will also be provided as an exploratory analysis
- DoR: Kaplan-Meier estimates such as median and Kaplan-Meier curves will be provided for patients who achieved a response (PR or CR, or PSA response for mCRPC patients)
- PFS: the PFS will be analyzed using the Kaplan-Meier method. The Kaplan-Meier estimates of the 25th, 50th and 75th percentiles and the 95% confidence intervals of median will also be computed. The Kaplan-Meier curves will be plotted. In addition, PFS at 6 months will also be provided

DCR \geq 6 months, PSA response rate, radiographic RR for mCRPC patients and ORR by iRECIST for NSCLC patients will be summarized with descriptive statistics. OS, time to response, and PFS by iRECIST will be analyzed using the Kaplan-Meier method. In addition, for mCRPC patients, rPFS, rPFS by iRECIST, duration of PSA response, duration of radiographic response, time to PSA response, time to radiographic response, and time to PSA progression will be also be analyzed using the Kaplan-Meier method.

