Tumor genetic markers (blood) W		Х			X (Cycle 2 and Cycle 3 only)	Х			
Immunophenotyping (blood) X		Х			X (Cycle 2, Cycle 3, then every other cycle)	Х	Х		
Plasma or serum cytokines (blood) y	Х	Х			X (Cycle 2, Cycle 3, then every other cycle)	Х	Х		
Disease Assessment									
- CT/MRI Z	Х				X (repeat every 9 weeks)	Х		Х	
- PSA assessment aa	Х	x k			X (repeat every 9 weeks)	Х		Х	
- Bone scan bb	Х				X (repeat every 9 weeks)	Х		Х	
Isatuximab Administration CC		Х	Χ	Χ	X				
REGN2810 Administration CC		Х			X				
AE/SAE Assessment dd	Х	Continuously throughout study period		iod			, new related AE/SAEs)		
Prior/Concomitant Medication	X (within 28 days prior to first dose)		Continuously throughout study period X (related to AE/SAEs)			AE/SAEs)			
New anticancer therapy						Х	>	1	Х
Survival status								Х	X

- a **Evaluation:** Assessments to be performed prior to study treatment and prior to premedication administration unless otherwise indicated. Inform consent should be signed before any study specific procedures. It can be signed more than 28 days prior to enrollment/randomization. Screening time indicates the time frame in which study procedures used to support eligibility have to be done prior to enrollment/randomization.
- b **Cycle:** A cycle is 21 days. The treatment window is ±1 day for each of the weekly administrations and ±2 day for each of the Q3W administrations. A dose is deemed to have been delayed if the treatment is ≥2 days beyond the theoretical day of treatment for Q3W dose. The window for blood chemistry, hematology, urinalysis, PSA assessment (Cycle 1 Day 1 only), and biomarker blood draw is within 1 day prior to IMP administration (where applicable) for Cycle 1 and beyond.
- c Follow-up: Patients who discontinue the study treatment without PD will be followed every 90 days for disease assessment until confirmation of PD or start of treatment with another anti-cancer therapy, or until study cut-off date, whichever comes first. The further follow-up schedule beyond 90 days after last dose of IMP is according to the disease progression status:
  - Patients who discontinue study treatment due to PD: phone call follow-up will be done every 90 days from the date of last IMP administration until death or study cut-off date.

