- x Immunophenotyping: a sample of peripheral blood will be drawn at Cycle 1 Day 1, Cycle 2 Day 1 and Cycle 3 Day 1 and then on Day 1 prior to IMP administration of each odd cycle starting from Cycle 5 (eg Cycle 5, Cycle 7, Cycle 9, Cycle 11, etc), at the EOT visit, and at follow-up (60 days after last IMP administration).
- y Plasma or serum cytokine concentration: A sample of peripheral blood will be drawn at baseline and Cycle 1 Day 1, Cycle 2 Day 1, Cycle 3 Day 1 and then on Day 1 prior to IMP administration at each odd cycle starting from Cycle 5 (ie, Cycle 5, Cycle 7, Cycle 9, Cycle 11 etc), at the EOT visit and at follow-up (60 days after last IMP administration).
- z Tumor assessment: CT or MRI of the chest, abdomen, pelvis and any other locations with suspicion or evidence of disease involvement is to be performed in all patients at screening (diagnostic quality scans performed as part of routine clinical management within 28 days prior to IMP initiation are acceptable). Repeat every 9 weeks starting at the end of Cycle 3 (63 ±7 days; disease assessment timing should follow calendar days and should not be adjusted for delays in cycle start), whenever disease progression is suspected, at the EOT visit (if not performed in the past 30 days) and during follow-up (if discontinue IMP without PD, repeat every 90 days), using the same method for each assessment. If tumor assessment status is partial or complete response, changes in tumor measurements must be confirmed by repeat assessments that should be performed no less than 4 weeks after the criteria for response are first met. Initial evidence of progression should be confirmed no less than 4 weeks later, see Section 6.7.1. Tumor assessment is not needed for patients who start another anti-cancer treatment regimen. Study sites must retain disease assessment images, as Sponsor may decide to collect these images for possible Independent Central Review in the future.

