- aa PSA assessment: For patients with mCRPC, to be performed at baseline (within 14 days before initiation of IMP). Repeat at Cycle 1 Day 1, every 9 weeks starting at the end of Cycle 3 (63 ±7 days; disease assessment timing should follow calendar days and should not be adjusted for delays in cycle start), at the EOT visit (if not performed in the past 30 days) and during follow-up (if discontinue IMP without PD, repeat every 90 days). PSA responses are to be confirmed no less than 4 weeks later. PSA assessment is not needed for patients who start another anti-cancer treatment regimen.
- bb Bone scan: Mandatory for patients with mCRPC (diagnostic quality scans performed as part of routine clinical management within 6 weeks prior to IMP initiation are acceptable). Repeat every 9 weeks at the end of Cycle 3 (63 ±7 days; disease assessment timing should follow calendar days and should not be adjusted for delays in cycle start), at the EOT visit (if not performed in the past 30 days) and during follow-up (if discontinue IMP without PD, repeat every 90 days). If progression is defined by bone scan only, the bone scan should be repeated no less than 6 weeks to confirm the progression, see Section 6.7.1. In case of doubtful lesions on bone scan, bone-centered X-ray or MRI scan should be performed to confirm the nature of those lesions (metastatic or not). Study sites must retain disease assessment images, as Sponsor may decide to collect these images for possible Independent Central Review in the future.
- cc REGN2810/Isatuximab Administration: At the start of each treatment cycle, the patient's weight will be determined. REGN2810 administration is only applicable in cohorts receiving isatuximab in combination with REGN2810.

Amended Clinical Trial Protocol No. 05 SAR650984-ACT15319 - isatuximab 11-Jun-2019 Version number: 1

dd AE/SAE assessment: All AEs, including adverse events of new onset as well as worsening of baseline signs and symptoms are to be reported from the signing of the informed consent to 30 days following the last administration of study treatment. After the 30 day all ongoing related non-serious AEs, ongoing SAE and new related AE/SAEs are to be followed to resolution or stabilization. Stabilization is defined as an AE ongoing without any change for at least 3 months. Severity will be graded according to NCI-CTCAE version 4.03.

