#### Disease assessment

- Tumor imaging: CT or MRI scan every 9 weeks starting at the end of Cycle 3 ( $63 \pm 7$  days) and whenever disease progression is suspected (the same method of assessment should be used throughout the study). Tumor imaging timing should follow calendar days and should not be adjusted for delays in cycle starts.
  - If initial evidence of RECIST 1.1 defined progression is documented, patients could continue treatment while waiting for PD confirmation scan 4 weeks after providing the patients are clinically stable as detailed in Section 6.7.1. When treatment is continued beyond RECIST 1.1 defined tumor progression, subsequent imaging assessments should be based upon iRECIST criteria (Appendix D).
  - For patients with mCRPC, bone lesions are not considered "non-measurable" lesion pre RECIST 1.1. Bone lesions will be assessed by bone scan only.
- Prostate-specific antigen assessment every 9 weeks starting at the end of Cycle 3 (63 ±7 days) for patients with mCRPC. Patients with PSA progression (Appendix A) in the absence of radiographic progression should continue IMP (local laboratory).
- Bone scan for patients with mCRPC, every 9 weeks starting at the end of Cycle 3 (63 ±7 days). In cases of PD based on bone scan only, the bone scan should be repeated after 6 weeks to confirm the progression using the 2+2 rule (2 new lesions on first scan, with at least 2 additional lesions on the confirmatory scan; refer to Appendix A) as detailed in Section 6.7.1. In case of doubtful lesions on bone scan, bone-centered X-ray or MRI scan should be performed to confirm the nature of those lesions (metastatic or not).

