2.1.3.3 Exploratory efficacy endpoint(s)

For patients with mCRPC and patients with NSCLC, the following endpoints will be summarized:

- Overall survival (OS): defined as the time from first study treatment administration to death for any cause. Patients without death prior to the analysis cut-off date will be censored at the last date the patient was known to be alive or the cut-off date, whichever comes first
- Time to response: defined as the time from first study treatment administration to the first response (PR or CR in radiographic objective response, or PSA decline $\geq 50\%$ for patients with mCRPC) that is subsequently confirmed (RECIST 1.1 for patient with NSCLC and PCWG3 criteria for patients with mCRPC)
- PFS by modified response evaluation criteria in solid tumors for immune based therapies (iRECIST) (3): is defined as the time from first study treatment administration to the date of first documented disease progression that is subsequently confirmed or the date of death from any cause, whichever occurs first. The same censoring rule as PFS will be used

In addition, the following endpoints will be summarized for patients with mCRPC:

- Disease control rate (DCR) ≥ 6 months: DCR ≥ 6 months includes patients with BOR of CR or PR of any duration or SD of ≥ 6 months duration. Duration of SD is defined as the time from the date of first treatment to the date of first disease progression or death due to any cause, whichever occurs first. Disease progression includes radiographic disease progression (per PCWG3 criteria) or unequivocal clinical progression. In the absence of disease progression or death before the analysis cut-off date or the date of initiation of a further anticancer treatment, the duration of SD will be censored at the date of the last valid disease assessment not showing disease progression performed prior to initiation of a further anticancer treatment and the analysis cut-off date, whichever is earlier

DCR ≥ 6 months rate is defined as the proportion of patients with DCR ≥ 6 months relative to the total number of patients in the analysis population

Similarly, DCR ≥ 6 months rate requiring PD confirmation will also be summarized

- Radiographic PFS (rPFS): For mCRPC patients, rPFS is defined as the time from first study treatment administration to the date of first documented radiographic progression or the date of death from any cause, whichever occurs first. The same censoring rule as PFS will be used

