2.4.8 Analyses of biomarker variables

The biomarker variables will be summarized by clinical group (eg, DCR ≥ 6 months for mCRPC patients vs. others) and overall. Graphics will be provided as appropriate. The biomarker variables include, but not limited to, the following variables:

- FCGR3A types: F/F, F/V, V/V and missing,
- CD38 expression
- PDL1 expression

Additional biomarker analysis may be conducted in an exploratory manner. Additional analysis, not specified in the protocol but related to the drug action and/or effect of isatuximab/REGN2810, may be conducted on remaining samples pending evolving literature.

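### Six months falls at the opening of the week-27 scan window, so PFS at 6 months leans towards week-18 status, and DCR ≥6 months can count patients whose week-27 scan shows progression

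*SAP*

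**What the plan says.** SAP 2.4.5.2 analyses PFS by Kaplan-Meier with quartiles and curves, and adds: "In addition, PFS at 6 months will also be provided". SAP 2.1.3.2 dates a PFS event at the first documented progression or at death. For mCRPC, unequivocal clinical progression also counts; for NSCLC it does not.

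SAP 2.1.3.3 defines an exploratory rate for mCRPC, DCR ≥6 months. It is met by CR or PR of any duration or by stable disease (SD) lasting at least six months: "Duration of SD is defined as the time from the date of first treatment to the date of first disease progression or death due to" (all causes of death count). Without an event, SD duration is censored at the last valid assessment free of progression. A second version requires progression to be confirmed. SAP 2.4.8 states "The biomarker variables will be summarized by clinical group", and its example of such a group is DCR ≥6 months.

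Protocol 1.3 sets the CT/MRI schedule: "Repeat every 9 weeks starting at the end of Cycle 3 (63 ±7 days; disease assessment timing should follow calendar days". Bone scans follow the same grid: "Repeat every 9 weeks at the end of Cycle 3 (63 ±7 days". Protocol 12.3.2 repeats it: "CT or MRI scan every 9 weeks starting at the end of Cycle 3".

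The SAP does not define six months in days. Its time-point windows (2.5.4) cover laboratory data only, and its section on data handling for secondary efficacy variables (2.5.2) is marked not applicable.

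**The concern.** A progression date is the date on which progression was seen, so a landmark estimate depends on where the landmark falls relative to the scans. Here it falls at the very start of a scan window. A patient who progresses between weeks 18 and 27, and is found only at the routine week-27 scan, is recorded as progression-free at six months although the first scan due around that time shows otherwise.

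The study has no control arm on the same schedule to absorb this, and single-arm 6-month figures invite comparison with other studies. For DCR ≥6 months the same patient enters the group described as having durable control, and so the benefit side of any biomarker summary that uses that grouping.

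**Working it through.** **Inputs from the documents.** "A cycle is 21 days" (Protocol 1.3), so the end of Cycle 3 is 3 × 21 = 63 days = 9 × 7 days. Scans are due at 63k ± 7 days. The cut-off for PFS is 12 months after the last patient's first treatment (SAP 2.4.5), so the week-27 scan lies within follow-up.

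**Assumptions, because the documents give no values.** Six months = 365.25/2 = 182.625 days (180 to 184 also tried). Progression time is exponential with a median of 2 to 9 months (30.4375 days each). The scan day is uniform over the 15 days of its window. A share q of events is documented when it happens (death, clinical progression in mCRPC, scan on suspicion); the rest are found at the next routine scan.

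**Step 1: the calendar.** Windows are days 56–70, 119–133, 182–196 and 245–259. No routine scan is due between day 133 and day 182. Of the 15 days in the week-27 window, the number at or before the landmark is 0 for a landmark at day 180, 1 at day 182 or 182.625, 2 at day 183, and 3 at day 184.

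**Step 2: the read-out when progression is found only at routine scans (q = 0).** True PFS is S(t) = 0.5^(t/m), with m the median in days. A patient reads as progression-free at six months if free at the week-18 scan, except for the 1 in 15 scanned on day 182. The read-out is therefore about (14/15)·S(126) + (1/15)·S(182).

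For a 3-month median, m = 91.3 days, S(126) = 0.384 and S(182) = 0.251. The read-out is 0.358 + 0.017 = 0.375, against a true S(182.625) of 0.250: an excess of 12.5 points. Simulating 400,000 patients per median gives the same value.

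**Step 3: events documented when they occur.** The excess becomes (1 − q) times the Step 2 excess. Simulated results, in percent or percentage points (differences may be off by 0.1 from rounding):

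| Median (months) | True PFS, 6 months | True PFS, day 126 | 6-month read-out, q = 0 | Excess, q = 0 | Excess, q = 0.5 | Excess, q = 0.75 | Read-out after day 196, q = 0 | True PFS, day 189 |
|---|---|---|---|---|---|---|---|---|
| 2 | 12.5 | 23.8 | 23.1 | 10.6 | 5.2 | 2.6 | 11.6 | 11.6 |
| 3 | 25.0 | 38.4 | 37.5 | 12.5 | 6.3 | 3.1 | 23.8 | 23.8 |
| 4 | 35.4 | 48.8 | 47.8 | 12.5 | 6.1 | 3.0 | 33.9 | 34.1 |
| 6 | 50.0 | 62.0 | 61.2 | 11.2 | 5.5 | 2.7 | 48.7 | 48.8 |
| 9 | 63.0 | 72.7 | 72.1 | 9.1 | 4.6 | 2.3 | 62.1 | 62.0 |

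The day chosen for six months matters little. For a 3-month median and q = 0, the excess is 38.4 − 25.5 = 12.9 points at day 180 and 35.7 − 24.7 = 11.0 at day 184. Read just after day 196, the curve is within 1.5 points of true 6-month PFS for every median shown.

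**Step 4: DCR ≥6 months.** Take two patients with SD at day 126.
- Patient A has progression first documented on day 189. SD duration is 189 days, above 182.6, so A counts as controlled.
- Patient B has no later valid scan and is censored near day 126. The SAP does not say how B is classified. Judged on observed duration, B does not count, even if truly stable at six months.

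A pushes the rate up and B pushes it down. If every patient is treated as SD and losses are independent of progression, the two cancel when the share lost before week 27 is 1 − S(182.625)/S(126). That is 1 − 0.250/0.384 = 35% for a 3-month median and 1 − 0.500/0.620 = 19% for a 6-month median.

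**The case against.** The grid is not the only source of progression dates. Protocol 1.3 also calls for CT/MRI "whenever disease progression is suspected, at the EOT visit (if not performed in the past 30 days) and during follow-up". Confirmatory imaging at least four weeks after a week-18 finding can fall from about day 154 (126 + 28). Deaths count as events in every cohort, and clinical progression counts in mCRPC. A reader might infer that no assessment at all takes place between days 133 and 182, or that the 6-month figure simply is week-18 status. The documents do not support either; only routine scheduled scans are absent. The 9–13 points are therefore the worst case.

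These routes help less than they first appear to. The suspicion clause is in the CT/MRI schedule but not in the bone-scan schedule. Confirmation of response concerns responders, not the SD patients behind DCR ≥6 months. Clinical progression is not an event for NSCLC PFS.

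It is also fair to say that the SAP defines PFS by documented progression, so the planned estimate is correct for its own definition and the excess is relative to unobserved progression time. The study is non-comparative, no 6-month threshold or test exists, and a drop at week 27 would show on the plotted curve. The PCWG3 table in Protocol Appendix A itself asks for 6- and 12-month proportions. All of this stands. It limits the consequence to interpretation and argues for keeping the 6-month figure with a second read-out beside it.

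**Conclusion.** The point holds for PFS at 6 months. Almost any progression first found at the routine week-27 scan is dated after the landmark, and nothing in the SAP adjusts for it. Under exponential PFS with medians of 2 to 9 months, the excess over true 6-month PFS is about 9–13 points if progression is found only at routine scans, 5–6 if half of events are documented when they occur, and 2–3 if three quarters are. The medians, the exponential form and these shares are assumptions.

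For DCR ≥6 months the point holds for the individual patient: SD at week 18 with progression first documented at week 27 counts as controlled for six months. A reader might infer that the rate as a whole is inflated, by an amount similar to PFS. That is not established. CR and PR count at any duration, and SD patients without a week-27 scan are censored near day 126 with no stated classification, which can offset the inflation or outweigh it.

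**What to change.** - **SAP 2.4.5.2:** keep PFS at 6 months and add the Kaplan-Meier estimate just after the week-27 window closes (28 weeks, after day 196), labelled as such.
- **SAP 2.1.3.3:** for the SD part of DCR ≥6 months, require a valid assessment on or after day 182 showing no progression. For the version that requires confirmed progression, require that this assessment shows no progression that is later confirmed. In both versions, count SD patients without such an assessment as not meeting the criterion.
- **SAP 2.4.8:** use this definition wherever DCR ≥6 months forms a biomarker group.

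The cost is SAP wording and one extra read-out, with no additional scans. The figures will be somewhat less favourable.

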2.1.3.2 Secondary efficacy endpoint(s)

The secondary efficacy endpoints are:

- Tumor burden change: Tumor burden change is defined as the best percent-change from baseline in a sum of the diameters (longest for non-nodal lesion, short axis for nodal lesions) for all target lesions

Area under the curve (AUC) of percent-change from baseline in tumor burden is defined as the area under the percent-change from baseline versus time curve calculated using the trapezoidal method from the date of the first post-baseline assessment to the date of the last assessment

The time-adjusted AUC of percent-change from baseline in tumor burden is defined as AUC of percent-change from baseline in tumor burden divided by the duration of the assessment

- Duration of response: Duration of response is defined as the time from the date of first response (PR or CR in radiographic objective response, or PSA decline $\geq 50\%$ for patients with mCRPC) that is subsequently confirmed to the date of first disease progression or death, whichever occurs first. Disease progression includes radiographic disease progression or unequivocal clinical progression. The RECIST 1.1 criteria will be followed for assessment of radiographic disease progression in patients with NSCLC and the PCWG3 criteria will be followed in patients with mCRPC. For patients with mCRPC, radiographic progression includes progression by PCWG3 modified RECIST 1.1 for soft tissue and/or PCWG3 defined progression by bone scan. In the absence of disease progression or death before the analysis cut-off date or the date of initiation of a further anticancer treatment, the DOR will be censored at the date of the last valid response assessment not showing disease progression performed prior to initiation of a further anticancer treatment and the analysis cut-off date, whichever is earlier. DOR will not be calculated for patients who do not achieve a response

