- rPFS by iRECIST: For mCRPC patients, rPFS is defined as the time from first study treatment administration to the date of first documented radiographic progression that is subsequently confirmed or the date of death from any cause, whichever occurs first. The same censoring rule as PFS will be used
- PSA response rate: defined as a PSA decline of $\geq 50\%$ from baseline that is subsequently confirmed
- Radiographic RR: defined as radiographic objective response assessed and confirmed by investigator

- Duration of PSA response: defined as the time from the date of the PSA first decline of $\geq 50\%$ from baseline that is subsequently confirmed to the date of first confirmed PSA progression or death, whichever occurs first. PSA progression for patients who have achieved a $\geq 50\%$ decrease from baseline is defined as at least a 25% increase and an absolute increase of ≥ 2 ng/mL above the nadir (the lowest PSA value on study). The same censoring rules as for DOR will be used
- Duration of radiographic response: defined as the time from the date of the first radiographic response (PR or CR) that is subsequently confirmed to the date of first radiographic progression or death, whichever occurs first. The same censoring rules as for DOR will be used
- Time to PSA response: defined as the time from first study treatment administration to the first PSA response that is subsequently confirmed
- Time to radiographic response: defined as the time from first study treatment administration to the first radiograph response that is subsequently confirmed
- Time to PSA progression: defined as the time from first study treatment administration to the date of first confirmed PSA progression. For patients who have achieved a $\geq 50\%$ decrease from baseline, PSA progression is defined as at least a 25% increase and an absolute increase of ≥ 2 ng/mL above the nadir (the lowest PSA value on study). For patients without a PSA decrease of this magnitude or no decrease at all, PSA progression is defined as at least a 25% increase and an absolute increase of ≥ 2 ng/mL above the baseline. Death from prostate cancer or any other cause without prior evidence of PSA progression will not count as an event. If no event exists, then time to PSA progression will be censored at the last scheduled PSA assessment on study or date of death, whichever occurs first

For patients with NSCLC, the following endpoint will also be summarized:

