2.4.5 Analyses of efficacy endpoints

All efficacy analysis will be performed using the all-treated population. In addition, efficacy analysis will be performed using the response evaluable population.

For each cohort, the analysis cut-off date for the primary analysis of RR will be 6 months after the last patient's first treatment in the cohort. The analysis cut-off date for secondary efficacy endpoints including DoR and PFS will be 12 months after the last patient's first treatment in the cohort. The primary analysis of RR will be updated.

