2.5.2 Data handling conventions for secondary efficacy variables

Not applicable.

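### The three time-to-response endpoints are planned by Kaplan-Meier on all treated patients with no censoring rule for non-responders; under the SAP's usual censoring the curves would overstate the proportion responding

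*SAP*

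**What the plan says.** SAP 2.4.5.2 names the method: "OS, time to response, and PFS by iRECIST will be analyzed using the Kaplan-Meier method". For mCRPC it adds that "time to PSA response, time to radiographic response, and time to PSA progression will be also be analyzed using the Kaplan-Meier method". No subset is named for any of the three response-time endpoints.

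The population comes from SAP 2.4.5: "All efficacy analysis will be performed using the all-treated population". The analyses are repeated on the response evaluable population, which also contains non-responders.

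The definition in SAP 2.1.3.3 gives only the start and the event: "Time to response: defined as the time from first study treatment administration to the first response", with the response later confirmed. Time to PSA response and time to radiographic response are defined in the same way, and Protocol 9.6.3 matches. None of these definitions has a censoring rule or mentions progression, death or new therapy.

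Duration of response is treated differently. SAP 2.1.3.2 says "DOR will not be calculated for patients who do not achieve a response", and SAP 2.4.5.2 says "Kaplan-Meier estimates such as median and Kaplan-Meier curves will be provided for patients who achieved a response".

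The section where a rule might have been placed, SAP 2.5.2 ("Data handling conventions for secondary efficacy variables"), is marked as not applicable. Protocol 13.4.4 leaves the detail of exploratory analyses to the SAP.

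**The concern.** Kaplan-Meier treats a censored patient as having the same later chance of the event as those still under observation. For response in this trial that is mostly untrue once a patient has progressed or died:

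- Under RECIST 1.1, as tabulated in Protocol Appendix D, a response cannot follow progression.
- After progression, follow-up is by telephone (Protocol 6.7.1 and 12.5.2). Off-treatment disease assessment continues only for patients who stopped without progression.
- For NSCLC, assessments after new anticancer therapy do not count towards best response (SAP 2.1.3.1).

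Progression and death without response are therefore competing events. If they are handled as censoring, each later response is given too much weight and one minus Kaplan-Meier drifts above the observed response rate. In a single-arm signal-search trial, the report could then show a response curve that ends above the response rate for the same patients.

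**Working it through.** **Step 1. The plan's own figures.** The plan states no figure for time to response. The response rates used below come from the Simon designs in Protocol Table 8, which reproduce under exact two-stage binomial sums:

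- mCRPC (10% vs 26%; 23 then 49 patients; at least 3, then at least 9 responses): alpha 0.0479, power 0.9015.
- NSCLC (5% vs 22%; 20 then 36 patients; at least 2, then at least 5 responses): alpha 0.0294, power 0.9018.

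The scan interval of 9 weeks is from Protocol 9.6.1.

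**Step 2. How the SAP censors elsewhere.**

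| Endpoint | Censoring point when there is no event |
|---|---|
| DOR, PFS | last valid assessment without progression |
| OS | last date known alive, or cut-off |
| Time to PSA progression | "If no event exists, then time to PSA progression will be censored at the last scheduled PSA assessment on study or date of death", whichever is first |
| Time to response (all three) | none stated |

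Carried over to time to response, the DOR, PFS and PSA-progression rules would remove a non-responder at about progression, last assessment or death.

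**Step 3. Illustration, 49 patients.** Assume 6 respond and 22 progress at week 9. Of the remaining 49 − 6 − 22 = 21, 3 respond at week 18. The total is 9 responders, which is the mCRPC final boundary.

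- Observed rate: 9/49 = 18.4%.
- Kaplan-Meier, the 22 censored at week 9: 1 − (1 − 6/49)(1 − 3/21) = 1 − (43/49)(18/21) = 24.8%.
- Kaplan-Meier, the 22 kept at risk to data cut-off: 1 − (43/49)(40/43) = 9/49 = 18.4%.
- Cumulative incidence with progression as competing event: 6/49 + (21/49)(3/21) = 9/49 = 18.4%.
- Responders only: 6/9 by week 9 and 9/9 by week 18. Nobody is censored, and the median is 9 weeks.

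**Step 4. Range over assumptions.** These inputs are not in the documents: responses at weeks 9, 18 and 27, split 60/30/10% or 40/30/30%; exponential time to progression or death in non-responders with median 2 to 6 months; no other loss. Expected-count results for where one minus Kaplan-Meier levels off:

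| True response rate | Censored at progression/death | Censored at the scan detecting progression | Censored at cut-off |
|---|---|---|---|
| NSCLC 22% | 29.6–60.9% | 24.8–41.4% | 22% |
| mCRPC 26% | 34.5–66.6% | 29.2–47.3% | 26% |
| NSCLC 5/36 = 13.9% | 19.2–45.6% | 15.7–28.0% | 13.9% |
| mCRPC 9/49 = 18.4% | 25.0–54.7% | 20.7–35.6% | 18.4% |

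The top of each range combines the shortest median (2 months) with the later split of responses. Given censoring at progression or death, or at the detecting scan, every scenario overstates. Only the amount is assumption.

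**The case against.** A reader might infer that the SAP prescribes a biased analysis. It does not go that far, because it writes no censoring rule for these endpoints. Step 3 shows that censoring non-responders at cut-off, or analysing responders only, removes the bias.

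Nor does the missing responder restriction prove that non-responders are included. The same Kaplan-Meier list contains duration of PSA response and duration of radiographic response, also without a restriction, and these can exist only in responders. The all-treated sentence nominally covers DOR too. The response-time endpoints are the ones in that list with no censoring rule, which fits a responder-only reading. These arguments stand and make the claim conditional.

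Three further inferences also fail:

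- Nothing says that time to response and response rate share a table, or that a one-minus-Kaplan-Meier plot is planned.
- A median that cannot be estimated in all treated patients is not a fault of Kaplan-Meier. With true rates of 22% or 26%, cumulative incidence would not reach 50% either.
- Patients do not all leave assessment at first progression. Clinically stable patients may continue until it is confirmed, and those with PSA progression alone stay on treatment. A PSA response can therefore follow unconfirmed radiographic progression.

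The objection does not supply the missing rule. Cut-off censoring appears nowhere for these endpoints, and a silent restriction to responders would depart from the all-treated statement. Two programmers could produce different curves, and the one who follows the SAP's usual pattern would overstate response.

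**Conclusion.** The point holds conditionally. The SAP names Kaplan-Meier for three response-time endpoints on all treated patients and leaves the handling of non-responders open. If they are censored as the SAP's other rules suggest, one minus Kaplan-Meier exceeds the proportion responding: 24.8% against 18.4% in the illustration, and by anything from under 2 to about 40 percentage points over the assumed range (15.7% vs 13.9% at one end, 66.6% vs 26% at the other). The documents give no progression rate, so they fix the direction under that censoring but not the size.

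The consequence is limited. The endpoints are exploratory, although their analysis is described under the secondary heading. The primary response rate is a proportion with a Clopper-Pearson interval, and it and the Simon decision rules are untouched. The change is still worth making, because it replaces an open and potentially misleading method with a defined one.

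**What to change.** In SAP 2.4.5.2, take the three response-time endpoints out of the Kaplan-Meier list and summarise them by median and range among confirmed responders. State in SAP 2.1.3.3 that they are calculated only for responders, as is already done for DOR.

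If a curve for all treated patients is wanted, use cumulative incidence, with progression, death and new anticancer therapy without prior response as competing events and data cut-off as administrative censoring. For PSA response, define the competing event as death, end of PSA assessment (other than by cut-off) or new anticancer therapy, because a PSA response can follow unconfirmed radiographic progression. The mCRPC composite has a PSA component and needs the same care.

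The cost is a few lines of SAP text and, for the descriptive option, simpler programming. No additional data are needed.
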